26.2 Calculations of outcomes

- The RMDQ-S is scored by summing up the number of items the patient checks.
- The SBI consists of four sciatica symptoms. Each symptom is rated 0-6 and a total bothersomeness score is obtained by summing up the ratings across the four symptoms
- The responder outcomes will be calculated as the change in leg pain scores between baseline and end of treatment, relative to baseline. Subjects with $\geq 30\%$ reduction in leg pain intensity will be classified as a 30% responder, others as non-responders. A similar procedure will be used to identify 50% responders.
- Use of weak opioids will be quantified using a weighted score by dividing the total dose taken from day 0 to day 10 by its respective DDD. The DDD is the assumed average maintenance dose per day for a drug used for its main indication in adults [3].
- Use of strong opioids will be quantified by the total dose converted into morphine milligram equivalents (MME) [4].

27 Analysis methods

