### 2.4 SECONDARY ENDPOINTS

- The change in back pain (24 hours average) rated on a 0-10 numeric rating scale (NRS) from baseline to day 10 based on longitudinal analyses of daily observations.
- The change in disability assessed by the Roland Morris Disability Questionnaire for sciatica (RMDQ-S) based on longitudinal analyses of observations at baseline, day 5 and day 10.
- The use of rescue medication, i.e. number of Paracetamol tablets taken between baseline and day 10.
- The number of patients who at day 5 and day 10 report their pain to be *completely gone, much better and better* on a Global Perceived Change (GPC) scale
- The change in sciatica symptoms assessed by the Sciatica Bothersomeness Index (SBI) based on longitudinal analyses of observations at baseline, day 5 and day 10.
- The number of patients who at day 5 and day 10 have a (i)  $\geq 30\%$  and a (ii)  $\geq 50\%$  reduction in leg pain score relative to baseline
- The use of (i) weak opioids and (ii) strong opioids assessed by the number of Defined Daily Doses (DDD) between baseline and day 10
- The number of patients who at day 10 are able to work/study as normal

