## 9.5 STATISTICAL ANALYSIS

### 9.5.1 Statistical methodology

The primary analyses will be performed by linear mixed effects models for repeated measures (MMRM) [88]. Mean changes from baseline will be analyzed using a restricted maximum likelihood (REML) based repeated measures approach. Analyses will include the categorical effects of treatment and treatment-by-visit interaction as fixed covariates and intercept as a random variable. Additionally, responder analyses comparing the percentage of patients who have

improved according to predefined cut-offs in the two groups (see 2.2), will be performed using a  $\chi^2$  test [89]. The strategy for dealing with missing values will be decided during the blind review of the data at the end of the trial. A statistical analysis plan will be prepared and made accessible at clinicaltrials.gov.

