13.2 Early stopping

The safety profile of Naproxen is well documented and established, and the dosing is under its approved label use. There is no reason to expect Naproxen to affect the rate of serious sciatica complications such as lower extremity paresis or cauda equina syndrome. As Naproxen is used under its approved label use no interim safety analyses will be conducted.

14 Timing of final analysis

All outcomes will be analyzed jointly after the end of the trial, i.e. after the last visit of the last subject, and data locking.

15 Timing of outcome assessments

Primary outcome: Leg pain (the primary outcome) is measured daily from baseline (day 0) to end of treatment (day 10).

Secondary outcomes

- Back pain is measured like leg pain
- Disability, assessed by the Roland Morris Disability Questionnaire for Sciatica (RMDQ-S), is measured at day 0, 5 and 10
- Rescue medication consumption is measured (i) at the end-of study-visit (by pill count) and (ii) daily from day 1 to day 10 (by self-report).
- Global perceived change is measured at day 5 and 10.
- Sciatica bothersomeness, assessed by the Sciatica Bothersomeness Index (SBI), is measured at day 0, 5 and 10.
- Concomitant use of opioid analgesics is assessed on day 0, 5 and 12 (± 2).
- The ability to work or study is measured at day 0 and 10.

Table 1. Timing of outcome assessments

	Baseline	Start of treatment				End of treatment	End of study
–							

Day	0	1	2-4	5 (± 1)	6-9	10	12 (± 2)
	Visit	Home	Home	Home	Home	Home	Visit
-Leg pain -Back pain	X	X	X	X	X	X	X
-SBI -RMDQ-S	X			X		X	X
Global perceived change				X		X	X
Work/study	X					X	X
Rescue medication (pill count)							X
Rescue medication (self-report)		X	X	X	X	X	
Opiod use	X			X			X

SBI Sciatica Bothersomeness Index, RMDQ-S Roland Morris Disability Questionnaire for Sciatica.

Visit windows.

Patient reported outcomes are captured using a web based real-time electronic diary (ViedocMe). The questionnaires are available 24 hours on the scheduled date. The end of study visit is scheduled on day 12 (± 2).

STATISTICAL PRINCIPLES

16 Level of statistical significance

A two-tailed p value of less than 0.05 is considered to indicate statistical significance. We will report nominal p values.

17 Adjustment for multiplicity

We will not adjust for multiple comparisons. This trial has one primary outcome which will be analyzed in a single mixed-effect model and there are no planned subgroup analyses.

18 Confidence intervals

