27.2 Analysis of secondary outcomes

- Back pain intensity will be analyzed using the same model used to analyze the primary outcome.
- Disability and sciatica bothersomeness will be analyzed using the same model used to analyze the primary outcome, but with 3 time points.
- Responder analyses, i.e. 30% and 50% improvement in leg pain intensity, will be performed using a mixed effects logistic regression model to obtain estimates of odds ratios (OR) and 95% CI. Based on the absolute risk reduction (ARR) between Naproxen and placebo we will calculate the numbers needed to treat (NNT) with 95% CI (NNT = 1/ARR).
- Rescue medication consumption and concomitant use of opioids during the treatment period will be analyzed using a suitable regression.
- Work/Study is an unordered categorical variable. The appropriate model is therefore a multinomial with repeated measurements and it will be analyzed using a GLMM.
- Global perceived change is an ordered categorical variable with repeated measurements and will be analyzed using a GLMM.

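### SAP 26.2 scores the 30% and 50% leg pain responders once per patient where the protocol scores them at day 5 and day 10, and SAP 27.2 names a mixed logistic model without its random effect or time points, so the size of the odds ratio may not be determined by the data

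*SAP*

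**What the plan says.** **Time points.** The responder item in protocol 2.4 begins "The number of patients who at day 5 and day 10 have a (i" and goes on to cut-offs of at least 30% and at least 50% reduction from baseline. SAP 26.2 has a single comparison: "The responder outcomes will be calculated as the change in leg pain scores between baseline and end of treatment, relative to baseline". SAP section 15 puts end of treatment at day 10. A patient who reaches the lower cut-off "will be classified as a 30% responder, others as non-responders", and the 50% cut-off is handled in the same way. Planned Table 2 has one row per cut-off and no day 5 row.

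**Method.** Protocol 9.5.1 compares the percentages of patients who "improved according to predefined cut-offs in the two groups (see 2.2), will be performed using a" chi-square test. SAP 27.2 says that the responder analyses "will be performed using a mixed effects logistic regression model to obtain estimates of odds ratios (OR) and 95% CI", and adds an NNT as the reciprocal of the ARR. It does not name the random effect, the time points, or the day to which the OR and NNT apply.

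**Random effects elsewhere.** SAP 27.1 justifies mixed models by the correlation between measurements on the same patient. SAP 27.3 leaves centre out of the main models. It allows centres only as additional random effects, if at least 4 centres recruit enough patients.

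**The concern.** There are two faults, and they are linked.

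First, the two documents define the endpoint at different times. The SAP gives no reason for leaving out day 5, although it keeps day 5 and day 10 for global perceived change, which protocol 2.4 defines on the same two days.

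Second, the model named in 27.2 does not fit the outcome defined in 26.2. A patient random intercept describes how outcomes within a patient resemble each other. With one binary outcome per patient, there is no such resemblance to observe.

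At stake are the OR and 95% CI for two secondary outcomes, which SAP 26.1 ranks as equal in importance to the others. The published OR could be near 2 or several times larger beside the same observed percentages and the same NNT. The day 5 comparison promised in the protocol might also not be reported.

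**Working it through.** **The plan's own figures.** The documents give no response rate, OR or power for the responder outcomes, so there is no responder figure to reproduce. The number of patients does reproduce. With a difference of 1.5, SD 2.5, two-sided 5% and 90% power, the two-sample t test needs 59.35, so 60 per arm (power 90.3%). Then 120/(1 − 0.20) = 150, or 75 per arm at 1:1.

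**Step 1: one binary value per patient, treatment only.** Let u be a normal patient intercept with SD σ, and let η₀ and η₁ be the log odds in the placebo and naproxen arms at u = 0. The response probability in arm j is

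P_j = E[ expit(η_j + u) ].

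The data enter the likelihood only through P₀ and P₁. For any σ, an η_j can be found that gives the observed proportion, so every σ reaches the same maximum. The reported OR is exp(η₁ − η₀), and this does change with σ.

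Assume 35% on placebo and 50% on naproxen, taken as exact proportions with 75 per arm. The maximised log-likelihood is 75 × [0.35 ln 0.35 + 0.65 ln 0.65 + 0.5 ln 0.5 + 0.5 ln 0.5] = −100.54 whatever σ is. At 50% symmetry gives η₁ = 0. Solving for η₀ by 80-point Gauss-Hermite quadrature, with a delta-method SE:

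| σ | η₀ | OR = exp(0 − η₀) | 95% CI | Wald z |
|---|---|---|---|---|
| 0 | −0.619 | 1.86 | 0.96 to 3.58 | 1.85 |
| 1 | −0.746 | 2.11 | 0.96 to 4.64 | 1.85 |
| 2 | −1.016 | 2.76 | 0.94 to 8.08 | 1.86 |
| 3 | −1.339 | 3.82 | 0.93 to 15.69 | 1.86 |
| 5 | −2.046 | 7.74 | 0.89 to 67.13 | 1.86 |

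The ARR is 0.50 − 0.35 = 0.15 and the NNT is 1/0.15 = 6.7 in every row.

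**Step 2: other assumed rates, σ from 0 to 5.**

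| Rates | OR | Wald z |
|---|---|---|
| 45% v 30% | 1.91 to 8.31 | 1.89 to 1.90 |
| 60% v 40% | 2.25 to 14.73 | 2.43 to 2.45 |
| 35% v 20% | 2.15 to 11.29 | 2.04 to 2.05 |

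**Step 3: adding baseline pain, age and sex.** Covariates identify σ only through the shape of the logistic curve. Three data sets of 150 patients were simulated with a true patient SD of 2. With the day 10 outcome alone, the log-likelihood moved by about 0.01 between σ = 0 and σ = 5. Over the same range the OR moved from 1.60 to 4.60, from 3.20 to 45.79, and from 1.29 to 2.31. For practical purposes σ remains unidentified.

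**Step 4: day 5 and day 10 together.** In the same data sets, with both outcomes and a treatment-by-day term, the log-likelihood peaked at σ of 1 or 2 on the grid 0, 1, 2, 3, 5. The gains over σ = 0 were:

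- 185.079 − 180.631 = 4.4
- 185.527 − 181.413 = 4.1
- 196.776 − 182.655 = 14.1

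So the patient random effect can be estimated once responder status is repeated.

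**The case against.** The strongest reply is that SAP 27.2 does not say the random effect is at patient level, and that a mixed model in this SAP usually signals repeated measurements. Leg pain is recorded daily, so responder status at several days may have been intended, and step 4 shows that such a model works. This stands as a possible reading. It does not remove the fault, because SAP 26.2 and planned Table 2 would then be wrong, and 27.2 would still need its days and random effect. The wording also leans the other way: the bullets on work/study and global change mention repeated measurements, and the responder bullet does not.

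A reader might infer that the odds ratio is simply arbitrary. That goes too far. Its direction and its Wald test come from the data and hardly vary with σ, and at σ = 0 the model is ordinary logistic regression. Planned Table 2 shows percentages and a difference, with no OR column. If those are the observed values, they do not depend on σ, and nor does the NNT. Only the size of the OR and its CI is undetermined.

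A reader might also take it as settled that day 5 has been abandoned, or that moving from chi-square to a model is itself an error. Neither follows. The first depends on which SAP section reflects the intent. On the second, protocol 9.5.1 announces a later SAP, and protocol 9.4 provides for deviations to be described and justified.

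SAP 27.4 allows other models if the data challenge the assumptions. That is limited protection, because a flat likelihood does not show which σ is wrong.

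**Conclusion.** The point holds in a limited form. The protocol and SAP differ on the responder time points, and SAP 26.2 and 27.2 do not fit together. Followed as written, with a patient intercept, the plan leaves the size of the OR and its CI undetermined: 1.86 to 7.74 at assumed rates of 50% v 35% for SDs of 0 to 5. Direction, test, observed percentages, ARR and NNT hardly change or do not change.

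This rests on two assumptions. The patient-level random effect is inferred from SAP 27.1 and 27.3, not stated. The response rates are assumed, because the documents give none. The non-identification itself does not depend on the rates; only the range of ORs does.

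The consequence is confined to the two responder outcomes. The primary analysis and the sample size are untouched. The text should be corrected before the analysis, since under either reading one SAP section has to change.

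**What to change.** - **SAP 26.2 and planned Table 2:** score the 30% and 50% responders at day 5 and at day 10, as in protocol 2.4, and name day 10 as the main time point.
- **SAP 27.2:** use ordinary logistic regression at each day, adjusted for baseline leg pain, age and gender. One repeated-measures model for both days with treatment-by-day is also acceptable, either GEE or a mixed logistic model with a stated patient random intercept.
- **Effect measures:** state the day to which the OR, ARR and NNT refer. Take the risk difference and NNT with 95% CI from the same model by standardisation, so that the measures agree.

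The cost is SAP wording and one added day 5 row per cut-off in Table 2. Daily leg pain scores are already collected, so no new data or patients are needed. If ordinary logistic regression or GEE is chosen, SAP 28.3 already assigns outcomes outside LMM and GLMM to multiple imputation; one sentence should confirm this for the responders.

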##### **5.4.2 Duration of Therapy**

The duration of therapy is 10 days.

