### 6.2.2 Washout

No specific washout procedure will be performed. However, at the day of inclusion patients will be encouraged to avoid analgetics/NSAIDs after bed time. Study medication will start the next morning.

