27.3 Adjustment for covariates

The statistical analyses of primary and secondary efficacy outcomes will be adjusted for baseline measures of the outcome where one is available [5]. The analysis of rescue medication consumption and use of concomitant opioids will be adjusted for baseline leg or back pain intensity depending on which is worse.

Study center (stratification variable) will not be included as covariate as we expect the majority of participants to be included at one center (Østfold). We will perform a sensitivity analysis with and without adjusting for center. Provided that a sufficient number of patients are included from at least 4 centers, these can be treated as additional random effects in the model.

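### The weak-opioid outcome counts day 0, before the first study dose; strong opioids have no window; and the only covariate named for opioid use is pain, at a cost mainly in precision

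*SAP*

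**What the plan says.** **Window.** SAP 26.2 computes the weak-opioid score by "dividing the total dose taken from day 0 to day 10 by its respective DDD". The strong-opioid bullet next to it converts total dose to morphine milligram equivalents and names no days. Protocol 2.4 has one definition for both classes, "assessed by the number of Defined Daily Doses (DDD) between baseline and day 10". SAP 27.2 words the analysis differently again: "Rescue medication consumption and concomitant use of opioids during the treatment period will be analyzed using a suitable regression".

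**Start of treatment.** Day 0 is the inclusion visit. Protocol 6.2.2 has no formal washout and states "Study medication will start the next morning"; the flow chart puts the start of treatment on day 1. Protocol 5.4.2: "The duration of therapy is 10 days".

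**Covariate.** SAP 27.3 first sets a general rule: efficacy outcomes are adjusted for their own baseline value where there is one. The next sentence, which also covers rescue medication, says that "use of concomitant opioids will be adjusted for baseline leg or back pain intensity depending on which is worse".

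**Data capture.** SAP section 15 says "Concomitant use of opioid analgesics is assessed on day 0, 5 and 12" (the last with a window of 2 days either side), and its timing table agrees. Protocol 5.3 and 6.5.5 instead have patients record other pain medication every day, by name and dosage.

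**The concern.** Opioid intake on day 0 cannot respond to a drug first taken the next morning, so it has no place in an outcome meant to capture opioid sparing. It is unlikely to be nil. Opioid users are expected at prescreening (protocol 4.3), analgesics are discouraged on day 0 only from bedtime, and other pain medication is discouraged, not barred, during treatment (protocol 5.3).

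The covariate matters more. Some patients will enter on opioids and others will not, and that difference is likely to persist over ten days. Day 0 use is the obvious variable to absorb it; a pain score need not track it closely. If the pain score is the only covariate, habitual use stays in the error term and the interval for opioid sparing is wider than it needs to be. Opioid sparing is a stated secondary objective, and SAP 26.1 ranks all secondary outcomes equally.

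**Working it through.** **The plan's own figure.** The only power calculation is for leg pain (protocol 9.1, SAP 11): difference 1.5, SD 2.5, two-sided 5%, 90% power. n per arm = 2 × (1.960 + 1.282)² × 2.5² / 1.5² = 58.4, so 59; the exact two-sample t test gives 59.35, so 60; and 120 / (1 − 0.20) = 150. It reproduces. No effect, SD or power is given for opioid use, so every opioid input below is an assumption.

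**1. Days counted.** Treatment covers days 1 to 10. The SAP 26.2 total covers days 0 to 10: 11 days, one of them before treatment.

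**2. Absolute difference.** Write the total as D0 + T, with T the intake on days 1-10. Randomisation makes the expected arm difference in D0 zero, so the expected difference in D0 + T equals that in T. Counting day 0 does not bias it.

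**3. Relative effect.** Let f be daily placebo use on days 1-10 relative to day 0, with a true ratio of 0.70. Observed ratio = (1 + 10f × 0.70) / (1 + 10f).
- f = 1 (stable use): 8 / 11 = 0.727. The 30% reduction appears as 27.3%, that is, shrunk by 1/11.
- f = 0.5: 4.5 / 6 = 0.750.
- f = 0.3: 3.1 / 4 = 0.775.

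**4. Standard error, no baseline-use adjustment.** Assume equal daily variance and a common day-to-day correlation r. Var(days 1-10) is proportional to 10(1 + 9r), and Var(days 0-10) to 11(1 + 10r).
- r = 0.3: √(44 / 37) = 1.090.
- r = 0.8: √(99 / 82) = 1.099.

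The standard error rises by 9-10%. For an effect that the day 1-10 total would detect with 80% power, power = Φ((1.960 + 0.842) / ratio − 1.960), which is 0.73 at r = 0.3 and 0.72 at r = 0.8.

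**5. Adjusting the day 1-10 total for day 0 use.** Correlation of day 0 with the total: c = 10r / √(10(1 + 9r)). Confidence interval width is multiplied by √(1 − c²).

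| r | c | CI width × | CI narrower by |
|---|---|---|---|
| 0.3 | 0.493 | 0.870 | 13% |
| 0.5 | 0.674 | 0.739 | 26% |
| 0.7 | 0.819 | 0.573 | 43% |
| 0.8 | 0.883 | 0.469 | 53% |

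A pain covariate with correlation 0.1 to 0.3 to opioid use gives √(1 − 0.01) = 0.995 to √(1 − 0.09) = 0.954, which is 0.5% to about 5% narrower.

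**6. The two issues together.** In a linear model with day 0 use as covariate in the same unit, adding D0 to the outcome raises the D0 coefficient by exactly 1 and leaves the treatment estimate and residuals unchanged.

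**7. Simulation check.** Assumed: 75 per arm, 30% users, mean use 1 DDD per day among users, a 30% reduction, skewed intake, 3,000 runs.

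| Outcome and model | Mean difference (DDD) | SD of estimate | Power |
|---|---|---|---|
| Days 1-10, unadjusted | −0.89 | 0.83 | 16% |
| Days 0-10, unadjusted | −0.89 | 0.93 | 13.5% |
| Either window, day 0 use as covariate | −0.87 | 0.39 | 66% |

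The median ratio moves from 0.70 to 0.73. The spread falls by a factor 0.387 / 0.833 = 0.46, so this setting sits near the r = 0.8 row of step 5, the favourable end.

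**The case against.** Three stronger readings are tempting, and the documents do not support them.

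*Counting day 0 pulls an opioid-sparing effect toward zero, so that a null result is partly built in.* Planned Table 2 in the SAP reports an absolute difference between arms, and step 2 shows that it is unaffected in expectation. Shrinkage appears only on a relative scale, which no section prescribes; SAP 27.2 leaves the regression open.

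*The whole opioid outcome counts day 0.* SAP 26.2 writes that window for weak opioids only. For strong opioids the defect is a missing window.

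*Pain replaces baseline opioid use.* SAP 27.3 does not say so. Read together, its two sentences can require both covariates, and in a linear model that would also remove the window problem (step 6). The defect is an unresolved ambiguity, though one that needs settling: read the other way, the only covariate is the weak one.

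Two practical objections have weight. First, a usable day 0 amount is not assured. Planned Table 1 shows baseline opioids as number and percentage only, and the baseline history covers 28 days. Yet the SAP 26.2 score itself cannot be computed without a day 0 dose, so either the covariate exists or the outcome has to be redefined anyway. Second, day 0 may be unrepresentative. Some opioid users are prescreened again 24 hours after their last dose, and analgesics are discouraged from bedtime on day 0. That lowers the plausible correlation, but at r = 0.3 the gain is still 13%. The gain from a yes/no covariate has not been calculated.

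**Conclusion.** The point holds as a matter of definition and precision. SAP 26.2 and 27.2 disagree on whether pre-treatment day 0 belongs in the weak-opioid total, strong opioids lack a window in 26.2, and 27.3 leaves open whether baseline opioid use is a covariate. The expected absolute difference is not biased. Without baseline-use adjustment, counting day 0 costs about 9-10% in standard error; a ratio of 0.70 would read as 0.73 under stable use, and nearer 0.75 to 0.78 if use fell to half or 30% of the day 0 level. The covariate is the larger matter: 13% to 53% off the interval width, against about 0.5% to 5% for pain.

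These sizes rest on assumed correlations, equal daily variance and a linear model for total dose; the documents give no opioid data and name no regression. One of several equally ranked secondary outcomes is affected. The primary result is not.

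**What to change.** - **SAP 26.2:** define both weak- and strong-opioid consumption from the first study dose (day 1) to day 10, in line with the treatment period in 27.2.
- **SAP 27.3:** state that day 0 opioid use is a covariate in the opioid analyses in addition to baseline pain, as an amount if recorded and otherwise as yes/no.
- **SAP 15 and its timing table:** reconcile the day 0, 5 and 12 assessment with the daily recording in protocol 5.3 and 6.5.5, and name the source of the day 1-10 total. If only the three contacts supply the data, whether days 1-10 can be separated depends on recall periods that the documents do not show.

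The cost is SAP text, a check of what the forms record, and one extra covariate.

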### 6.2.5 Final Study Visit

At day 12 ( $\pm 2$ ) or within 7 days after withdrawal there will be a final study visit at the clinic. Patients will return all pill boxes for pill count. Questionnaires, vital signs, adverse events and laboratory tests will be performed.

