# **9 STATISTICAL METHODS AND DATA ANALYSIS**

## **9.1 DETERMINATION OF SAMPLE SIZE**

The sample size calculation is based on a mean difference between the Naproxen group and the placebo group of 1.5 (0-10) at ten days with a SD of 2.5 using a two-sample t test. There is no robust evidence for the smallest worthwhile

between group pain relieving effect in sciatica. In previous sciatica studies sample size were calculated based on between group differences of 1.5 and 1.0 [80, 81]. In a recent RCT of pregabalin the sample size was calculated based on a between group difference of 1.5 [36]. In knee osteoarthritis, a condition in which NSAIDs are generally recommended, the treatment effect of NSAIDs is about 1.0 [82-84]. The estimated SD of 2,5 is based on a recent Cochrane review of NSAID studies in sciatica [30].

Assuming 90% power and a two-tailed 5% significance level a sample size of 60 subjects is needed in each treatment arm. Allowing for a combined dropout and non-compliance rate  $\leq 20\%$  [85] the total number of subjects will be 150.

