8.2 Secondary objectives

To demonstrate that, in patients with sciatica, treatment with Naproxen 500 mg twice daily is superior to placebo with respect to

- improvement in back pain intensity
- improvement in disability
- use of rescue medication
- global perceived change in sciatica/back problem
- improvement in sciatica symptom bothersomeness
- 30% and 50% improvement in leg pain
- concomitant use of opioid analgesics
- ability to work and study

STUDY METHODS

9 Trial Design

NIS is a multicenter, two-armed randomized, placebo controlled, double blind, parallel group, superiority phase IV trial.

10 Randomization

Study medicines will be packaged and labelled according to a pre-generated random number sequence; each sealed box will have a unique participant number. Computer-generated block randomization, stratified by center, will be used. Allocation to Naproxen or placebo will be at a 1:1 ratio.

11 Sample size

The sample size estimation is based on a minimum difference of interest between the Naproxen group and the placebo group of 1.5 at day 10. Assuming a standard deviation SD of 2.5 (see protocol for details and references), 90% power and a two-tailed 5% significance level, 60 subjects in each treatment arm is required. Allowing for a combined dropout and non-compliance rate $\leq 20\%$ a sample size of 150 was determined.

12 Framework

Analyses will be within a superiority hypothesis testing framework, comparing Naproxen to placebo.

13 Interim analyses and stopping guidance

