Demographic and clinical characteristics will be summarised by assigned treatment group without comparisons, as shown in 32.1 (Planned table 1). Categorical variables will be summarised by frequencies and percentages. Percentages will be calculated according to the number of patients for whom data are available. Where values are missing, the denominator, which will be less than the number of patients assigned to the treatment group, will be reported either in the body or a footnote in the summary table. Continuous variables will be summarised by mean and standard deviation, or by medians and interquartile range (IQR).

ANALYSIS

26 Outcome definitions

26.1 Specification of outcomes.

The primary outcome is leg pain intensity (24 hours average), rated on a 0-10 NRS. Higher scores indicate more severe pain.

Secondary outcomes:

- Back pain intensity (24 hours average), rated on a 0-10 NRS.
- Disability, measured by RMDQ-S (0-23), higher scores indicate worse disability.
- Sciatica bothersomeness, measured by the SBI (0-24), higher scores indicate more symptom bothersomeness.
- $\geq 30\%$ improvement in leg pain score
- $\geq 50\%$ improvement in leg pain score
- Global perceived change measured on a 7-point Likert scale (sciatica/back problem completely gone, much better, better, a little better, no change, a little worse, worse and much worse).
- Rescue medication consumption, measured by pill count, i.e. the number of Paracetamol pills not returned at the end of study. If the Paracetamol package is not returned, self-report data from the electronic diary will be used. Higher rescue consumption indicates more pain.
- Concomitant use of opioids, higher consumption indicate more pain
- Ability to work or study full time, measured by 3 nominal categories (unable, able, other)

We consider the secondary outcomes to have equal importance.

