28.3 Statistical methods to handle missing data

The LMM and GLMM statistical models for analysis of the primary outcome and continuous secondary outcomes assume that missing data follow a missing at random (MAR) pattern, in which the probability of missingness may depend on other observed outcome values in the model, but are not related to the unobserved values of missing responses themselves. For outcomes not analyzed using likelihood-based methods (LMM and GLMM) missing data will be handled using multiple imputation (MI). MI will also be used in sensitivity analyses, see above (27.6).

MI under MAR or MCAR will initially be performed separately within each treatment arm. The models will include all variables in the analytic models plus the values of all baseline characteristics reported in Table 1. A total of 50 imputed data sets will be created. Pooled estimates will be calculated using Rubin's rules.

29 Additional analyses

29.1 Assessment of patient blinding.

At the end of treatment (day 10), or withdrawal, patients are asked to guess what treatment they have received. The response categories include (i) Naproxen, (ii) placebo and (iii) don't know. Descriptive data (2x3 table) will be presented, no statistical analyses will be performed.

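### Rescue and opioid use are raw totals with no rule for patients observed for only part of the period, so a truncated total can be analysed as if complete

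*SAP*

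**What the plan says.** SAP 26.2 quantifies weak opioids by "dividing the total dose taken from day 0 to day 10 by its respective DDD". Strong opioids are the total dose in morphine equivalents, with no window stated. SAP 26.1 defines rescue use as a count of tablets not handed back and turns to the diary only when the package is not returned. More use is read as more pain ("Concomitant use of opioids, higher consumption indicate more pain", and likewise for rescue).

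SAP 27.2 leaves the regression model for both outcomes open. The only covariate named in SAP 27.3 is the worse of baseline leg or back pain. No exposure term, offset or minimum recording period appears.

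On return of the boxes, Protocol 6.2.5 says: "At day 12 ( $\pm 2$ ) or within 7 days after withdrawal there will be a final study visit at the clinic". The flow chart in Protocol 6.1 lists box return at the withdrawal visit. Protocol 5.8 lets the pill count prevail where it disagrees with the diary.

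On follow-up, SAP 28.1 intends to go on collecting data after withdrawal, and Protocol 6.4.1 continues the full schedule for patients who stop only the study drug. SAP 28.3 sends missing data to multiple imputation for outcomes that are not analysed by a linear or generalised linear mixed model.

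**The concern.** A total is comparable between patients only if it covers the same days. A patient who leaves on day 4 and hands in the box has a tablet count for four days, and it stands beside ten-day counts. Because the count is an available number, an analyst who follows 26.1 would use it, and the imputation in 28.3 would have nothing to act on. For opioids the position is less settled: the SAP does not say whether a dose recorded over part of days 0–10 is the patient's value or an incomplete one.

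Two stated secondary objectives are at stake. If early exit is more frequent in one arm, and those who leave use more (or less) medication than those who stay, the truncation shifts the difference between arms. The open model also leaves the handling to be chosen after the data have been seen.

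**Working it through.** **The plan's own figure.** The documents give no effect size or power for these two outcomes. The stated sample size concerns leg pain (difference 1.5, SD 2.5, 90% power, two-sided 5%). It reproduces: the two-sample t test needs 59.35, so 60 per arm, and 120 / (1 − 0.20) = 150. The present point does not touch it.

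**Which rule applies to whom.**
- Stops the study drug only: recording and the final visit continue (Protocol 6.4.1), so the total should be complete.
- Leaves and returns the box before day 10: the count is the outcome (SAP 26.1) and prevails over the diary (Protocol 5.8). The value is truncated but not missing.
- Leaves and does not return the box: the diary is summed. The SAP does not say what happens to days without a record.
- Leaves and opioid recording ends: the SAP is silent on whether the partial dose is complete.

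**Per patient, at a constant rate of use.** Opioids recorded from day 0 to day k cover (k + 1)/11 of the period: 4/11 = 36%, 5/11 = 45% and 6/11 = 55% for k = 3, 4 and 5. For paracetamol at the ceiling of 6 tablets per 24 hours (Protocol 5.2.1), the ten-day total is 60. A box returned after day 3, 4 or 5 gives 18, 24 or 30. A completer taking 1.8, 2.4 or 3.0 tablets a day gives the same counts.

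**Between arms, opioids.** All rates here are assumed. 15% of placebo and 5% of naproxen patients leave after day 4. Leavers use 0.6 DDD/day; stayers use 0.30 (placebo) or 0.25 (naproxen).
- Full totals over 11 days: leavers 6.60, placebo stayers 3.30, naproxen stayers 2.75.
- True means: placebo 0.85 × 3.30 + 0.15 × 6.60 = 3.795; naproxen 0.95 × 2.75 + 0.05 × 6.60 = 2.943. Difference 0.853.
- Counted means, with leavers at 5 × 0.6 = 3.0: placebo 2.805 + 0.450 = 3.255; naproxen 2.613 + 0.150 = 2.763. Difference 0.493, a loss of 1 − 0.493/0.853 = 42%.
- With 10% leaving in both arms: true 3.630 − 3.135 = 0.495; counted 3.270 − 2.775 = 0.495. Both means are too low, but the difference is unbiased.

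**Between arms, rescue.** Assumed: naproxen patients and placebo stayers take 3 tablets/day, and a share of the placebo arm takes 6/day and returns the box early.
- Returned after day 3 by 10%: true 0.9 × 30 + 0.1 × 60 − 30 = +3.0; counted 0.9 × 30 + 0.1 × 18 − 30 = −1.2. With 5% and 20% leaving, +1.5 and +6.0 become −0.6 and −2.4.
- Returned after day 5: the counted difference is 0 in all three cases.
- With 2 tablets/day instead of 3, and return after day 5: +2, +4 and +8 shrink to +0.5, +1.0 and +2.0.

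**Would a rate model repair it?** With arm alone and a log(days) offset, a quasi-Poisson model estimates total dose over total days. In the opioid example, mean days are 0.85 × 11 + 0.15 × 5 = 10.1 for placebo and 0.95 × 11 + 0.05 × 5 = 10.7 for naproxen. The rates are 3.255/10.1 = 0.3223 and 2.7625/10.7 = 0.2582. Over 11 days the difference is 0.705, still 17% short of 0.853, because heavy users who leave contribute few days.

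**Would imputing the whole total repair it?** If leavers' totals were drawn as though they were stayers, the difference would be 3.30 − 2.75 = 0.55, which is 35% short. The days observed before exit have to inform the imputation.

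**The case against.** The strongest reply is that the plan keeps collecting data. SAP 28.1 says so generally, and Protocol 6.4.1 keeps patients who stop only the study drug on the full schedule. Someone who stops because the drug does not help may well be in that group. Others are invited to report by eCRF or phone. A box may come back up to seven days after withdrawal, so a patient leaving on day 3 could return it on day 10 with a complete count. For weak opioids the outcome is defined over days 0–10, so a careful analyst could call a shorter total missing and impute it under 28.3.

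All of this stands, and it narrows the problem to patients whose follow-up really ends or whose box comes back early. It does not remove it. Protocol 6.3 allows discontinuation from assessments as well as treatment, and Protocol 6.2.6 only encourages withdrawn patients to attend. Continued diary entries do not rescue the tablet count, because the count prevails.

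A reader might infer that the SAP scores unrecorded days as zero, or that early leavers necessarily get the lowest totals. The documents support neither. No passage says that a partial opioid total is complete. In the example above, leavers score 3.0 DDD, above naproxen stayers (2.75) and below placebo stayers (3.30). Nor do the documents show that exit for lack of effect will be more common on placebo: it is not a coded withdrawal reason in SAP 24, and rescue and other pain medication are available to everyone.

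**Conclusion.** The gap is real and limited. For rescue use, the written rules produce a truncated outcome whenever the box is returned before day 10. For opioids, the SAP leaves open whether a partial total is complete. In both cases the patient's use is understated. The comparison is biased only if early exit differs between arms and goes with medication use.

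The size cannot be derived from the documents. The assumed scenarios run from no bias (equal exit, equal use among leavers) through a 42% loss to a reversed sign. The planned 20% allowance combines dropout with non-compliance and says nothing about exit by arm. The primary outcome and the sample size are unaffected. Because these are stated secondary objectives, and SAP 26.1 gives all secondary outcomes equal importance, the rule should be settled before unblinding.

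**What to change.** Amend SAP 26.2, 27.2 and 28.3:

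- State that a rescue or opioid total that does not cover the period to day 10 is incomplete, and give the window for strong opioids as well.
- Treat unobserved days as missing, and multiply impute daily use before summing. Add the patient's recorded daily use to the imputation model, which in 28.3 lists only the analysis variables and baseline characteristics.
- When the box is returned before day 10, use the diary for days 1–10 instead of the pill count, as a stated exception to Protocol 5.8.
- Name the daily record in Protocol 5.3 and 6.5.5 as the source for opioids; SAP 15 lists assessments only at days 0, 5 and 12.
- Report days observed by arm beside the totals.
- Keep a rate model with a log(days) offset as a sensitivity analysis only, since it assumes that use after exit equals use before it and down-weights early leavers.

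The cost is SAP wording and somewhat more analysis, with data the protocol already collects daily. The result relies on missing at random given recorded use, and early returners are measured by diary while others are measured by pill count.
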